Specific Aim 3. Examine the effects of an AFO following a walking exercise program. The device may improve primary and secondary outcomes following 12 weeks of community walking (standard of care). Outcomes will include PWT, COT, functional ability, VO_{2peak} and patient-reported outcomes assessed with the Walking Impairment Questionnaire (WIQ) and the Medical Outcomes Study Short Form 36-item questionnaire (SF-36).

B. Study Design and power calculation

B.1. Study design

The proposal will utilize a prospective cohort design. We will recruit a total of 15 male and female patients with PAD and IC who are ≥40 years of age. Patients will be diagnosed with PAD at the vascular clinics of the International Heart Institute (IHI) within St. Patrick Hospital and its affiliated outreach sites within their network of providers or will be screened per standard guidelines if not receiving care from IHI (see **D.2.d. Ankle-brachial index assessment**).

B.2. Power calculation

Sample size was calculated to evaluate differences in PWT with the AFO vs. without during graded exercise testing. The estimates were based on data from a previously conducted clinical trial¹⁴ composed of 25 PAD patients who were randomized to a new detailed community-based walking program or the standard of care (upfront advice to exercise). Based on an effect size of 0.94, a sample of 12 patients is estimated to provide 80% power at α =0.05 to detect a significant difference in PWT. To account for a 20% attrition rate, 3 additional patients are needed (total sample n=15).

C. Patient recruitment and inclusion/exclusion criteria

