Primary recruitment sites will be from the IHI clinics in Missoula, MT as well as IHI's clinical outreach sites throughout Western Montana and Idaho. This includes the following locations: 1) IHI at Community Hospital Anaconda, MT, 2) IHI-Butte, MT, 3) IHI at Powell County Medical Center, Deer Lodge, MT, 4) IHI at Marcus Daly Memorial Hospital, Hamilton, MT, 5) IHI-Helena, MT, 6) IHI-Plains, MT, 7) IHI at St. Joseph Medical Center, Polson, MT, 8) IHI at St. Luke Community Clinic, Ronan, MT, 9) IHI at Steele Memorial Hospital, Salmon, ID, 10) IHI at Seeley-Swan Medical Center, Seeley Lake, MT, 11) IHI at Life Span Medical Clinic, Stevensville, MT and 12) IHI at Thompson Falls, MT. Additionally patients will be recruited from the physical therapy clinics at the University of Montana and in the local community via posted advertisements and emails to the University and hospital communities. The study doctor and Co-Investigator [name] will medically approve all patients for inclusion into the trial.

Patients will be provided a copy of the consent. Patients will meet with the study staff who will explain the study to them and discuss their primary reasons and motivation for wanting to volunteer in the trial. The study team will also discuss any practical problems such as planned vacations that could interfere with completion of the trial in a timely manner. Any questions the patients have regarding the trial will be answered and the patients must demonstrate their ability to provide informed consent by describing in detail their understanding of the study goals and what is expected of them. Patients are given a signed copy of the consent form, with signed copies placed in separate study charts (separate from PHI). A HIPAA authorization form will also be obtained from patients during the first study visit. All research study team members have completed relevant protection of human subjects' modules per regulatory standards.

C.1. Exclusion criteria

- Lower extremity amputation(s) which interfere(s) with walking.
- Critical limb ischemia (i.e., ischemic rest pain, ulcers/gangrene on the lower extremities).
- Non-atherosclerotic PAD (e.g., popliteal entrapment syndrome, Takayasu's arteritis)
- Major surgical procedures that are contraindicated to an exercise program (e.g., recent organ transplant) or coronary artery bypass graft within 6 months prior to screening.

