- Primarily limitations to exercise due to chronic obstructive pulmonary disease, angina or heart failure.
- Myocardial infarction within 3 months prior to screening.
- Acute coronary syndrome symptoms diagnosed at time of screening.
- Significant ischemic changes (documented on the 12-lead electrocardiogram) which horizontal or down-sloping ST-segment depression ≥0.5 mm at rest and >1 mm with exercise in 3 beats for 2 contiguous leads, relative to the PR-segment (or ST-segment elevation ≥1 mm).
- Transient ischemic attack or stroke 3 months prior to screening.
- New left bundle branch block or sustained ventricular tachycardia of >30 seconds during screening.
- Uncontrolled hypertension defined as \ge 180 systolic or \ge 100 diastolic resting blood pressure during screening.
- Woman who are pregnant (women of childbearing potential, a pregnancy test will be performed at screening).
- Individuals currently incarcerated.
- Evidence of acute impairment from alcohol or other illicit drugs.
- Lack of diabetes control (glycated hemoglobin >12%).
- Patients who are anemic (Hgb $<11 \text{ g}\cdot\text{dL}^{-1}$ for women and $<10 \text{ g}\cdot\text{dL}^{-1}$ for men).

- Any other clinically significant diseases (e.g., pulmonary, renal, psychiatric, immunological) that are not stabilized or may otherwise confound the results of the study.
- Individuals meeting exclusion criteria may still be recruited into trial with the approval for participation by a physician.

D. Methods

D.1. AFO: We will provide patients with two AFO devices (one for each leg). Prior mechanical analysis of walking in PAD revealed deficits in both limbs for ankle power production for those who experience IC.¹⁵ We will use a standard carbon-fiber AFO model (see Figure 1) that is commercially available to enhance the clinical meaningfulness of the pilot trial (see section **G. Measures to minimize potential risks and discomforts** below for patient fitting details). The design of this AFO provides considerable energy storage potential to maximize the effect of the calf muscle augmentation in this initial pilot project.

Figure 1. Example of carbon-fiber AFO for use in walking exercise

D.2. Assessments and Outcomes

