- **D.2.a.** Health history and physical exam: Patients will complete a health history form (attached). Questions pertaining to their health and any recent adverse events will be discussed with each patient. The initial health history examination is important for reviewing inclusion/exclusion criteria for the study. Height and weight will be recorded, followed by a physical exam conducted by a physician/PA/NP (unless extensive medical records in EPIC available). Calf and quadriceps muscle circumferences will be measured at baseline and at 12 week outcome visits using a constant tension spring loaded tape.
- **D.2.b. Vital signs:** Vital signs will be assessed at all outcome assessment study visits. This will include resting heart rate (beats·min⁻1), standing systolic and diastolic blood pressure (mmHg) and sitting blood pressure using a standard electronic or manual sphygmomanometer. Patients will be asked to breathe normally while the study team performs the assessments.
- **D.2.c. Blood draws:** Patients will be asked to fast for 10 hours prior to outcomes assessment visits. Six teaspoons of blood will be drawn from the patient to assess the following: 1) complete blood count, 2) glycated hemoglobin, and 3) lipid panel.
- **D.2.d. Ankle-brachial index (ABI) assessment:** ABIs will be performed prior to the initial graded exercise test according to published methods for screening purposes and standard outcome assessment. ¹⁶ Measurements will be of the left and right systolic pressures for 1) brachial arteries, 2) dorsalis pedis arteries, and 3) posterior tibial arteries. The method utilizes a Doppler ultrasound to detect the systolic blood pressure. The highest of the arm pressures is used as the denominator. The numerator for the ABI of each ankle is derived from the highest of the dorsalis pedis or posterior tibial pressures. The leg with the lowest ABI is identified as the index leg. *Note that in the event a patient has not been diagnosed with PAD, a separate ABI assessment may need to be completed prior to fitting the patient for the AFO devices.*

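### The anaemia exclusion in C.1 is looser for men (Hgb <10 g/dL) than for women (<11 g/dL), the reverse of what a sex-specific limit should do

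*Combined protocol and SAP*

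**What the plan says.** The protocol's list of exclusions (C.1) includes "Patients who are anemic (Hgb $<11 \text{ g}\cdot\text{dL}^{-1}$ for women and $<10 \text{ g}\cdot\text{dL}^{-1}$ for men". This is the only haemoglobin limit in the documents, and it comes with no reason or reference. Both sexes are enrolled: B.1 states "We will recruit a total of 15 male and female patients".

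Several clauses bear on how the limit works in practice:

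- Section C says that the study doctor "will medically approve all patients for inclusion into the trial".
- C.1 has a general exclusion: "Any other clinically significant diseases (e.g., pulmonary, renal, psychiatric, immunological) that are not stabilized or may otherwise confound the results of the study".
- The last bullet of C.1 is an override: "Individuals meeting exclusion criteria may still be recruited into trial with the approval for participation by a physician".
- D.2.a uses the health history to review eligibility, followed by a physical examination unless extensive electronic records exist.
- D.2.c obtains the haemoglobin value from a blood draw covering "1) complete blood count, 2) glycated hemoglobin, and 3) lipid panel".
- Section G removes patients who cannot complete the graded test safely because of an abnormal event.

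**The concern.** A limit that differs by sex should follow a difference in what is normal for each sex. Men's normal haemoglobin is generally taken to be the higher, so a man at, say, 10.5 g/dL is at least as far below his norm as a woman at 10.5 g/dL is below hers. The printed rule flags her and not him.

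At stake is the screening of men before exertion. The criterion presumably protects patients who will walk to their limit on a graded treadmill test, and it is applied less strictly to the sex for which a given value is the more abnormal. On the female side there is no safety cost, only an exclusion that a physician can waive.

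**Working it through.** The plan has no calculated figure to reproduce here, so the check applies the rule as printed.

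**Inputs.** Female limit 11 g/dL and male limit 10 g/dL (C.1); 15 patients of both sexes (B.1); visit schedule (Table 2).

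**Step 1: who is excluded.** Applying the rule in steps of 0.1 g/dL from 9.5 to 11.5 gives:

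| Haemoglobin (g/dL) | Woman | Man |
|---|---|---|
| below 10.0 | excluded | excluded |
| 10.0 to <11.0 | excluded | not excluded |
| 11.0 and above | not excluded | not excluded |

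The band in which the sexes differ is 11.0 − 10.0 = 1.0 g/dL wide.

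**Step 2: which standard could produce this order.** Let d be the male minus the female normal haemoglobin. The documents do not give d, so it is an assumption. With F the female norm, the depth below the norm at the limit is F + d − 10 for men and F − 11 for women. The difference is (F + d − 10) − (F − 11) = d + 1.

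- The rule is even-handed only at d = −1, that is, if men's norm were 1 g/dL lower than women's.
- Over an assumed range d = 0, 1, 2 the difference is 1, 2, 3 g/dL.
- With a common limit of 11 the difference is (F + d − 11) − (F − 11) = d, giving 0, 1, 2 over the same range.

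This is the printed gap of 1 g/dL plus an assumed d. It shows only that the direction is wrong for any d of 0 or more, and it is not an effect size for the trial.

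**Step 3: exposure.** Table 2 marks a graded test at Visits 2, 3, 4 and 5, so a man in the band can face up to 4 such tests without having met the anaemia criterion.

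**Step 4: what the other clauses do.** The override acts on patients who meet an exclusion. It can admit a woman in the band but has nothing to act on for a man in it. The study doctor's approval, the general exclusion and the history and examination can each stop such a man, but by case-by-case judgement. The removal rule in Section G acts only once a test has gone wrong. None of them changes the printed limits.

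**Step 5: what is not touched.** Aim 1 compares each patient with and without the device at two baseline visits within a week (D.2.e), so a patient's haemoglobin status is largely common to both conditions. The sample size in B.2 rests on an effect size, power, alpha and attrition; haemoglobin does not enter.

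**The case against.** The strongest case on the other side is that the limit hardly matters. Every patient is medically approved, a man with clinically important anaemia can be refused under the general exclusion, and the tests run under continuous ECG with staff trained in advanced life support. With 15 patients, perhaps nobody will have a value in the band. The claim that the direction is wrong also needs a physiological premise that the documents do not supply. Most of this stands, and it is why the point is minor. It does not supply a reason for the printed order, and discretionary review is no ground for leaving a written limit uncorrected.

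Four stronger readings are tempting, and the documents do not support them:

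- **The two labels were transposed.** This is plausible, but no source or alternative limit is given, so it cannot be established.
- **A man at 10.0 to <11.0 g/dL is unsafe on this test.** Nothing in the documents shows that. The point is only that the protocol's own limit is applied unevenly.
- **The results are biased.** Aim 1 is a within-patient contrast. For Aim 3, the documents do not give the historical cohort's haemoglobin criteria, so no effect can be claimed.
- **Haemoglobin is unknown at the first test.** Table 2 puts the blood draw and the first graded test both at Visit 2 without an order, whereas D.2.d says "ABIs will be performed prior to the initial graded exercise test". Silence about order does not show that the result comes too late, and a chart value may exist. That question is also separate from the sex-specific limits.

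**Conclusion.** The concern holds as a minor defect in an eligibility criterion. The asymmetry is certain from the text: within a band of 1.0 g/dL a woman is excluded, subject to physician approval, and a man is not flagged. That the direction is wrong rests on one assumption, that normal haemoglobin is not lower in men than in women. How often such values occur is not in the documents, so no probability is given; few, possibly none, of the 15 patients would be affected. The consequence is confined to eligibility and safety at exercise testing.

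**What to change.** Amend C.1 so that the male limit is not below the female limit. By default use <11 g/dL for both sexes and keep the physician-approval clause. A common limit removes the reversal, although it does not adjust for a sex difference in norms.

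Ask the sponsor to check where the criterion came from. Exchange the labels (women <10 g/dL, men <11 g/dL) only if that source confirms a transposition, because the exchange would admit women at 10.0 to <11.0 g/dL whom the protocol now excludes, and so would loosen a safety criterion.

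The cost is a one-line amendment; the complete blood count is already drawn. The downside of the default is that a man at 10.0 to <11.0 g/dL would need physician approval to enter, which could cost a small trial an occasional recruit.

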- Graded exercise test: [name] (PI) has extensive experience in clinical exercise testing and training for patients with PAD. The IHI has a full complement of Advanced Cardiovascular Life Support (ACLS) certified healthcare providers (e.g., cardiologists, physician assistants, nurse practitioners) to monitor exercise stress test electrocardiograms for patients enrolled into the trial. [name] is the study doctor for this trial and will provide oversight of stress testing. IHI has necessary resuscitative equipment (e.g. crash carts) and trained personnel available if a patient experiences an adverse event during exercise testing. Additionally, in the event of an acute myocardial infarction during exercise testing, the IHI Cardiac Catheterization laboratory is ~50 meters from the Montana PACE lab. The stress tests are critically important for determining the safety of any exercise activity the patients will complete. The likelihood of an adverse event caused by exercise training is most likely to occur during the stress test when the critical equipment and personnel are available to respond to such an event. Patients who are unable to safely complete the graded exercise test due to an abnormal event will be categorized as high risk and excluded from participation in the trial. The dryness of the mouth and throat will be minimized by allowing the patient to drink water prior to the test as needed. A thorough description of the device will be explained to patients' (informed the mouthpiece is similar to "snorkel" or "mouth guard") and that slight bleeding of the gums from contact with the mouthpiece is not serious and common during use.
- Vulnerable populations: Pregnant woman may not be included in this study. Pregnancy testing will be requested if their menstrual cycle is more than one week overdue or if they suspect they are pregnant. We don't anticipate this

- being a concern, as the average age of PAD patients is in the mid-60's and thus the vast majority of women PAD patients are post-menopausal.

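### The closing waiver in section C.1 leaves four acute cardiac/ECG exclusions open to override before the first maximal treadmill test, and it is inconsistent with section G's bar on pregnancy

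*Combined protocol and SAP*

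**What the plan says.** The exclusion list in section C.1 ends with a bullet that reverses it at a physician's discretion: "Individuals meeting exclusion criteria may still be recruited into trial with the approval for participation by a physician". It carries no exceptions or conditions.

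Among the criteria above it are four that concern acute cardiac or ECG findings:

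- On conduction and rhythm: "New left bundle branch block or sustained ventricular tachycardia of >30 seconds during screening"
- On a recent infarct: "Myocardial infarction within 3 months prior to screening"
- On ischemia, covering ST changes both at rest and with exercise: "Significant ischemic changes (documented on the 12-lead electrocardiogram"
- On unstable symptoms: "Acute coronary syndrome symptoms diagnosed at time of screening"

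Pregnancy is also on the C.1 list.

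Three other statements bear on how far the waiver reaches. Section C has the study doctor give medical approval for every patient who enters. Section G, under vulnerable populations, says "Pregnant woman may not be included in this study", with no provision for override. Section G, under the graded exercise test, has a removal rule: "Patients who are unable to safely complete the graded exercise test due to an abnormal event will be categorized as high risk and excluded".

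**The concern.** The four acute cardiac/ECG criteria exist to keep certain patients off a treadmill. The primary outcome, peak walking time, comes from a graded test in which the patient walks for as long as severe leg pain allows (D.2.e). An exclusion that can be set aside for any patient, with no category held back, is only advice at the point where it matters most. As written, a patient known to have had an infarction in the previous 3 months, or with new LBBB (left bundle branch block), could be approved for that test without any departure from the protocol.

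Pregnancy raises a different problem. C.1 read alone allows an exception and section G allows none, so site staff have two rules and no statement of which one governs.

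The stake is patient safety and clear eligibility rules. The point does not bear on the sample size or on the analysis of peak walking time.

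**Working it through.** No formula applies. The check is a count and a comparison of the relevant texts.

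**1. Count of criteria under the waiver.** The first four bullets of C.1 cover amputation, critical limb ischemia, non-atherosclerotic disease, and major surgery or bypass. Thirteen more follow: cardiopulmonary limitation, infarction, acute coronary syndrome (ACS), ischemic ECG changes, stroke or TIA, LBBB or ventricular tachycardia (VT), hypertension, pregnancy, incarceration, alcohol or drug impairment, diabetes control, anemia, and other unstable disease. That gives 4 + 13 = 17. The waiver bullet itself exempts 0 of the 17.

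**2. What limits the waiver, criterion by criterion.**

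| Criterion | Exempted in the C.1 bullet | Limit before the first treadmill test | Limit once a test is attempted |
|---|---|---|---|
| Infarction in prior 3 months | No | Study doctor's approval (C) | Removal rule (G) |
| ACS symptoms | No | Study doctor's approval (C) | Removal rule (G) |
| Ischemic ECG changes at rest | No | Study doctor's approval (C) | Removal rule (G) |
| New LBBB or sustained VT | No | Study doctor's approval (C) | Removal rule (G) |
| Pregnancy | No | Study doctor's approval (C) and outright bar (G) | Not needed if G governs |

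For the four cardiac/ECG rows, the only limit before the test is a discretionary one. For pregnancy there is an absolute rule elsewhere, but C.1 does not refer to it.

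**3. Timing.** The schedule of visits in D.3 gives Visit 1 to consent, orthosis fitting, heart rate and blood pressure, and an ankle-brachial index where PAD is undiagnosed. The health history, the ECG and the first graded test are all at Visit 2, and D.2.a makes the health history a basis for the eligibility review. A waiver decision can therefore fall on the day of the first test. Graded tests are marked at Visits 2, 3, 4 and 5, which makes 4 per patient. The removal rule cannot act until test 1 has started. A waived patient who completes test 1 safely is not caught by it and goes on to the remaining 4 − 1 = 3.

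**4. Reach of the proposed change.** Making the four cardiac/ECG criteria and pregnancy absolute protects 4 + 1 = 5 of 17 and leaves 17 − 5 = 12 open to waiver. The change cannot prevent the first test for ST changes that first appear during exercise at Visit 2. For those, it governs only the 3 later tests.

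**5. Size of the risk.** The protocol's only event rate, in section F, is about 6 per 10,000 tests in a mixed adult population. It gives no rate for patients who meet these exclusions and no expected number of waivers. No estimate of added risk follows from those inputs.

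**The case against.** The strongest reply is that section C already supplies the gate. The study doctor's approval covers every patient, including anyone recruited under the last bullet, and it acts before inclusion. Harm would require the study doctor knowingly to approve someone with, say, active ACS symptoms for treadmill testing, and nothing in the protocol suggests that is intended. Much of this stands. A reader might infer from the bullet's unspecified physician that any doctor could admit a patient past the study doctor; read with section C, the documents do not support that. What remains is that the approval is discretionary and makes no criterion absolute.

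A second reply is that section G surrounds the test with safeguards: ECG monitoring by ACLS-certified staff, resuscitation equipment and a nearby catheterization laboratory. Section G does say that an exercise-related event is most likely during the stress test, but its argument there is that this is when help is at hand. That is fair. These measures detect and treat an event, though; they do not keep out a patient whose condition is already known.

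A third reply is that pregnancy is already settled. A reader might infer that the waiver opens the trial to pregnant women. The documents do not support that: section G bars them outright, and a specific prohibition would ordinarily limit a general permission. The fault is an inconsistency between two sections. Few candidates are likely to be affected, since entry is at age 40 or over and section G expects most women with PAD to be post-menopausal.

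Finally, choosing which criteria to make absolute involves judgement. Recent stroke and severe hypertension, for example, also bear on treadmill safety and would remain waivable. The narrow list is defensible because it covers the acute cardiac and ECG findings most directly tied to the test, plus the one criterion on which the protocol contradicts itself.

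**Conclusion.** The point holds in a limited form. The waiver exempts none of the 17 criteria. For the four acute cardiac/ECG criteria, no text makes exclusion absolute before the first treadmill test. For pregnancy, C.1 and section G are inconsistent and should be aligned.

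This rests on reading the bullet by its plain words and on treating the study doctor's approval as a real but discretionary check. The scenario also requires the condition to be known before the patient starts the Visit 2 test.

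A reader might try to size the problem by carrying section F's event rate across the four scheduled tests. That would describe any participant in a mixed adult population and would be the same with or without the waiver, so it does not measure this defect. The added risk is unquantified. The case for the change is that it is specific, cheap and protective, not that events are predicted.

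**What to change.** Amend the last bullet of C.1 so that the physician's waiver cannot cover five criteria: infarction within the preceding 3 months, ACS symptoms at screening, ischemic ECG changes, new LBBB or sustained VT, and pregnancy. In the same bullet, say that the approving physician is the study doctor, in line with section C. Add one sentence stating that the exclusions in section G prevail over any waiver. Note in the amendment that, for ST changes first seen during exercise at Visit 2, the rule applies from the next graded test onward.

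The cost is a short text amendment, with no new visits or procedures. The downside is slightly less recruitment flexibility in a 15-patient pilot; the other 12 criteria stay open to waiver.
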